5.1 Enrollment/screening period

All screening and enrollment procedures will be performed according to the assessment schedule in [Appendix B Table 1](#). Demographic data and other characteristics will be recorded including date of birth or age, gender, smoking history, and race/ethnicity, according to local regulations. A standard medical and surgical history will be obtained.

Written informed consent and any locally required privacy act document authorization must be obtained prior to performing any protocol-specific procedures, including screening/baseline evaluations. If laboratory or imaging procedures were performed for other reasons prior to signing consent, these can be used for screening purposes with consent of the patient. However, all screening laboratory and imaging results must have been obtained within 28 days of enrollment. All patients will have the option to provide consent to supply a sample of their tumor (archived or newly acquired biopsy) for entry into this study. This consent is included in the main patient informed consent form.

Screening/baseline evaluations may be performed over more than 1 visit.

The timing of vital sign assessments should be such that it allows the blood draw (eg, PK blood sample) to occur at the time points indicated in [Appendix B Table 1](#).

5.2 Treatment period

All procedures to be conducted during the treatment period will be performed according to the assessment schedule (see [Appendix B Table 1](#)).

Whenever vital signs and blood draws are scheduled for the same nominal time, the assessments should occur in the following order: vital signs and then blood draws. The timing of the vital signs assessments should be such that it allows the blood draw (eg, PK blood sample) to occur at the time points indicated in [Appendix B Table 1](#).

5.3 Follow-up period

All procedures to be conducted during the follow-up period will be performed according to the assessment schedule [Appendix B Table 1](#)).

6. STUDY ASSESSMENTS

Please also refer to Section 6 of the master protocol for the study assessments applicable to all arms in the study. Additional study assessments applicable to Arm B are listed below.

6.1 Safety Assessments

6.1.1 Laboratory safety assessments

The laboratory variables to be measured are presented in [Table 2](#) (clinical chemistry), [Table 3](#) (hematology), and [Table 4](#) (urinalysis).

Other safety tests to be performed at screening include assessment for hepatitis B surface antigen, hepatitis C antibodies, and human immunodeficiency virus antibodies.

The following laboratory variables will be measured:

Appendix B Table 2 Laboratory - clinical chemistry

Albumin	Lipase ^b
Alkaline phosphatase ^a	Magnesium ^c
ALT ^a	Potassium
Amylase ^b	Sodium
AST ^a	Total bilirubin ^a
Bicarbonate ^c	Total protein
Calcium	TSH
Chloride ^c	T3 free ^d (reflex)
Creatinine clearance ^c	T4 free ^d (reflex)
Creatinine	Urea or blood urea nitrogen, depending on local practice
Gamma glutamyltransferase ^c	
Glucose	
Lactate dehydrogenase	

^a Tests for ALT, AST, alkaline phosphatase, and total bilirubin must be conducted and assessed concurrently. If total bilirubin is >2 × upper limit of normal (and evidence of Gilbert’s syndrome), then fractionate it into direct and indirect bilirubin.

^b It is preferable that both amylase and lipase parameters are assessed. For sites where only 1 of these parameters is routinely measured, then either lipase or amylase is acceptable.

^c Bicarbonate (where available), chloride, creatinine clearance, gamma glutamyltransferase, and magnesium testing are to be performed at screening, on Day 1 (unless screening laboratory assessments are performed within 3 days prior to Day 1), and if clinically indicated.

^d Free T3 and T4 will only be measured in Arm A if TSH is abnormal or if there is a clinical suspicion of an AE related to the endocrine system.

AE Adverse event; ALT Alanine aminotransferase; AST Aspartate aminotransferase; T3 Triiodothyronine; T4 Thyroxine; TSH Thyroid-stimulating hormone.

Appendix B Table 3 Laboratory – hematology

Basophils	Monocytes
Eosinophils	Neutrophils
Hematocrit	Platelet count
Hemoglobin	Red blood cell count
Lymphocytes	Total while blood cell count
Mean corpuscular hemoglobin	Activated partial thromboplastin time
Mean corpuscular hemoglobin concentration	International Normalized Ratio
Mean corpuscular volume	Partial thromboplastin time

Note: For coagulation parameters, activated partial thromboplastin time, partial thromboplastin time and international normalized ratio are to be assessed at baseline and as clinically indicated.

Note: absolute values of blood cells should be provided where possible rather than percentages (e.g. for white cell differential counts)

Appendix B Table 4 Laboratory – urinalysis

Bilirubin	Ketones
Blood	pH
Color and appearance	Protein
Glucose	Specific gravity

Note: Urinalysis must be done at baseline and then as clinically indicated.

Note: Microscopy should be used as appropriate to investigate white blood cells and use the high power field for red blood cells.

6.1.2 ECG

A 12-lead safety ECG (paper ECG printout of 10 seconds for Investigator review) will be taken at screening and prior to dosing on day 1 of each study cycle.

Triplicate ECG recordings should be taken within an approximate 5-minute period. Additional ECGs may be taken at any other time the Investigator deems necessary for safety during the administration period. The patients will rest for at least 10 minutes before the start of each recording and they must be in the same supine body position (maximum 30 degrees flexion in the hip and feet not in contact with the footboard) at the recording time point.

The Investigator will judge the overall interpretation as normal or abnormal. If abnormal, it will be decided as to whether or not the abnormality is clinically significant or not clinically significant. The paper copy of each ECG reading will be retained with the patient’s completed source documents. Only overall evaluation (normal/abnormal) will be recorded in the eCRF. If there is a clinically significant abnormal unscheduled ECG finding during the treatment

period, this should be recorded on the AE eCRF, according to standard AE collection and reporting processes (see Section 7).

Attention should be paid to any detected increases in QTc interval. Patients who develop a single resting value of QTc interval of >450 msec/male and >470 msec/female or a shift from baseline of ≥ 60 ms should stop taking AZD1775. Dosing can be resumed at a reduced dose after return of the resting QTc interval to pre-treatment status has been confirmed and correction of possible electrolyte imbalance has been made (see [Appendix B Table](#)).

Monitoring of QTc, checking and correction of abnormal electrolyte levels and renal function are advised, especially in case of severe/prolonged diarrhoea. If QTc increases markedly from baseline, but stays below the above limits, a cardiologist’s advice should be sought.

The concomitant use of ondansetron (known to prolong the QTc interval in rare cases, per labelling) should be taken into account when interpreting QTc changes.

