9.4.2.2 Safety assessments

For the change from baseline summaries for vital signs, laboratory data, ECGs, and physical examination, the baseline value will be the latest result obtained prior to the start of study treatment.

The QTcF will be derived during creation of the reporting database using the reported ECG values (RR and QT).

$QTcF = QT / RR^{(1/3)}$ where RR is in seconds

Corrected calcium will be derived during creation of the reporting database using the following formulas:

$Corrected\ calcium\ (mmol/L) = Total\ calcium\ (mmol/L) + ([40 - albumin\ (G/L)] \times 0.02)$.

The denominator used in laboratory summaries will only include evaluable patients, in other words, those who had sufficient data to have the possibility of an abnormality.

For example:

- If a CTCAE criterion involves a change from baseline, evaluable patients would have both a pre-dose and at least 1 post-dose value recorded.
- If a CTCAE criterion does not consider changes from baseline, to be evaluable, the patient need only have 1 post dose-value recorded.

The denominator in vital signs data should include only those patients with recorded data.

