13. Patient has had prescription or non-prescription drugs or other products known to be sensitive to cytochrome P450 (CYP)3A4 substrates or CYP3A4 substrates with a narrow therapeutic index, or to be moderate to strong inhibitors/inducers of CYP3A4 which cannot be discontinued 2 weeks prior to the first day of study drug dosing and withheld throughout the study until 2 weeks after the last dose of study drug. Coadministration of aprepitant or fosaprepitant during this study is prohibited. The use of sensitive substrates of CYP3A4, such as atorvastatin, simvastatin and lovastatin, is also prohibited in this study. As grapefruit and Seville oranges are known to contain moderate inhibitors of CYP3A4, these fruits or their products (including marmalade, juice, etc.) should be avoided while taking AZD1775. (see Appendix I Disallowed Medications and Medications to be Administered with Caution). Transporter studies (in vitro) have shown that AZD1775 is an inhibitor of breast cancer resistance protein (BRCP). The use of rosuvastatin in this study is prohibited.
14. Herbal preparations are not allowed throughout the study. These herbal medications include but are not limited to: St. John's wort, kava, ephedra (ma hung), ginkgo biloba, dehydroepiandrosterone (DHEA), yohimbe, saw palmetto and ginseng. Patients should stop using these herbal medications 7 days prior to first dose of study treatment.
15. Patients with Grade ≥ 2 neuropathy will be evaluated on a case-by-case basis after consultation with AstraZeneca Study Physician.
16. Patient with mean resting corrected QT interval (specifically QTc calculated using the Fridericia formula) > 470 msec from 3 ECGs performed within 5 minutes apart at study entry or congenital long QT syndrome.
17. Any of the following cardiac diseases currently or within the last 6 months as defined by New York Heart Association \geq Class 2 ([Appendix B1 New York Heart Association Criteria](#))
18.).
 - Unstable angina pectoris
 - Congestive heart failure
 - Acute myocardial infarction
 - Conduction abnormality not controlled with pacemaker or medication
 - Significant ventricular or supraventricular arrhythmias (patients with chronic rate-controlled atrial fibrillation in the absence of other cardiac abnormalities are eligible)
18. AZD1775 should not be given to patients who have a history of Torsades de pointes unless all risk factors that contributed to Torsades have been corrected (see Section

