Appendix B Table 9 Non-hematologic toxicity dose modification and management

Electrocardiogram QT corrected interval prolonged		
QTc Value	CBDP	AZD1775
QTc 450-480 ms (males) or 470-480 (females)	No dose modifications	Hold. Once QTc interval has returned to pretreatment status and correction of possible electrolyte imbalance has been made, resume at next lower dose level.
QTc 481-500 ms	No dose modifications	Hold. Seek cardiologist advice.

QTc \geq 501 ms	Discontinue treatment	Discontinue treatment
Shift from baseline of \geq 60ms	Discontinue treatment	Discontinue treatment
<hr/>		
CTCAE version 4.03	CBDP	AZD1775
Grade 0 - 2	No dose modification	No dose modification
Grade 3 ^{b,c,d}	Hold ^a	Hold ^a
Grade 4 ^b	Hold until toxicity resolves to Grade \leq 1. Resume with 1 dose level reduction	Hold until toxicity resolves to Grade \leq 1. Resume with 1 dose level reduction
Second repeat incidence of Grade 3 or 4 toxicity (except nausea, vomiting, fatigue, malaise, lethargy, anorexia, alopecia)	Discontinue treatment	Discontinue treatment
<hr/>		
Hepatic		
<hr/>		
CTCAE v4.03	CBDP	AZD1775
Grade 1-2	No dose modification	No dose modification
Grade 3 or 4 (manifested as elevations in ALT, AST, ALP, or bilirubin)	Hold until resolves to Grade \leq 1 or baseline, then resume CBDP with a 1 level dose reduction. If not resolved within 28 days, discontinue CBDP.	Hold until resolves to Grade \leq 1 or baseline, then resume study drug with a 1 level dose reduction. If not resolved within 28 days, discontinue study drug.
<hr/>		
Diarrhea or mucositis		
<hr/>		
CTCAE v4.03	CBDP	AZD1775
Grade 1-2	No dose modification	No dose modification
Grade 3 or 4 (or requiring hospitalization)	Hold ^a	Hold ^a
<hr/>		
Nephrotoxicity		
<hr/>		
CTCAE v4.03	CBDP	AZD1775
Grade 0-1	No dose modification	No dose modification

Grade ≥ 2 Hold until resolves to Grade ≤ 1 or Hold^a
baseline, then resume CBDP with
a 1 level dose reduction. If not
resolved within 28 days,
discontinue CBDP.

Neurotoxicity		
CTCAE v4.03	CBDP	AZD1775
Grade 1	No dose modification	No dose modification
Grade 2	Hold until toxicity resolves to Grade ≤ 1 . Resume with 1 dose level reduction.	No dose modification
Grade 3 or 4	Discontinue treatment	Discontinue treatment

- ^a Hold until toxicity resolves to \leq Grade 1 and then resume at the same dose with no modification.
- ^b Dose reduction for nausea and vomiting should be made only if Grade 3 or Grade 4 toxicity occurs in spite of maximum anti-emetics.

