9. STATISTICAL ANALYSES BY ASTRAZENECA

Please refer to Section 9 of the master protocol for details regarding statistical analyses applicable to all arms. Additional details regarding statistical analyses applicable to Arm B are described below.

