7.1.3 ECG

Triplicate ECG recordings are required within 7 days prior to starting study treatment (i.e., during screening), as well as at the times as shown in the study plan.

Triplicate ECG recordings should be taken within an approximate 5-minute period. Additional ECGs may be taken at any other time the Investigator deems necessary for safety during the administration period. The patients will rest for at least 10 minutes before the start of each recording and they must be in the same supine body position (maximum 30 degrees flexion in the hip and feet not in contact with the footboard) at the recording time point. The Investigator or designated physician will review the paper copies of each of the timed 12-lead ECGs on each of the study days when they are collected and assess whether they are clinically significantly abnormal/ not clinically significantly abnormal. If there is a clinically significant abnormal finding, the Investigator will record it as an AE on the eCRF. For information on recording of AEs see Section 7.3. The original ECG traces must be stored in the patient medical record as source data.

A standardised ECG machine should be used and the patient should be examined using the same machine throughout the study, where feasible. ECGs will be recorded at 25 mm/sec. Attention should be paid to any detected increases in QTc interval. Patients who develop a single resting value of QTc interval of >450 msec/male and >470 msec/female or a shift from baseline of 60ms should stop taking the study treatment. Dosing can be resumed at a reduced dose after return of the resting QTc interval to pre-treatment status has been confirmed and correction of possible electrolyte imbalance has been made. Monitoring of QTc, checking and correction of abnormal electrolyte levels and renal function are advised, especially in case of severe/prolonged diarrhoea. If QTc increases markedly from baseline, but stays below the above limits, a cardiologist's advice should be sought and Sponsor should be contacted for advice and notification. The concomitant use of ondansetron (known to prolong the QTc interval in rare cases, per labelling) should be taken into account when interpreting QTc changes.

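### Appendix B 6.1.2 keeps the numbers needed for QTcF out of the Arm B eCRF, and its general rule for resuming AZD1775 contradicts Table 9 on QTc

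*Protocol*

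**What the plan says.** **ECG data.** Appendix B 6.1.2 has a paper 12-lead ECG taken at screening and before dosing on Day 1 of each cycle, and read by the investigator. On storage it says "The paper copy of each ECG reading will be retained" with the source documents, and on data entry "Only overall evaluation (normal/abnormal) will be recorded in the eCRF". Master Section 9.4.2.2 says "The QTcF will be derived during creation of the reporting database using the reported ECG values (RR and QT"), with the formula QT / RR^(1/3), and lists ECGs among the change-from-baseline summaries. Appendix B Section 9 sends the reader to Section 9 "of the master protocol for details regarding statistical analyses applicable to all arms". The only Arm B addition there is a window for adverse events.

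**Dose action.** Appendix B 6.1.2 stops AZD1775 for a single resting QTc above 450 ms (men) or 470 ms (women), or for a shift from baseline of 60 ms or more. It then says: "Dosing can be resumed at a reduced dose after return of the resting QTc interval to pre-treatment status has been confirmed", provided any electrolyte imbalance has also been corrected. Appendix B Table 9 divides the same territory into four categories with different actions. One of them is the row that begins "Shift from baseline of" and covers shifts of 60 ms or more. Appendix B 7.3.3.6 says that the QTc dose actions are summarised in an Appendix B table. Table 9 is the only Arm B table with QTc rows.

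**The concern.** QTcF needs two numbers per tracing, and the Arm B data-entry rule lets neither into the database. Appendix B 2.4.2 lists QT prolongation among the reported safety concerns for AZD1775, and 7.3.3.6 calls for an assessment of any emerging QTc prolongation. At stake is whether the report can give a QTcF value or a numeric change for this arm. An abnormal reading alone does not separate a QTc change from any other ECG abnormality.

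The second issue bears on patients. If 6.1.2 and Table 9 prescribe different actions for the same QTc result, two sites that both follow the protocol can treat the same patient differently: one re-doses AZD1775 at a lower level, the other stops both drugs permanently.

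**Working it through.** **1. Can QTcF be produced for Arm B?**

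- Inputs needed (9.4.2.2): QT and RR, both numeric, for QTcF = QT / RR^(1/3).
- QT or RR values entered in the eCRF (Appendix B 6.1.2): 0. Only the overall evaluation is entered.
- Other routes: neither a central reader nor a digital ECG transfer is described for Arm B.
- Exemption: none in Appendix B Section 9.

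The derivation therefore has no input for Arm B as specified. A shift table of normal and abnormal readings remains possible, and would satisfy the general mention of ECG change from baseline in 9.4.2.2. What fails is QTcF and its numeric change.

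The values do exist at the sites. Appendix B exclusion criterion 16 needs a mean Fridericia QTc "from 3 ECGs performed within 5 minutes apart at study entry", and the paper tracings are kept. The gap can be closed from existing material.

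**Size of that repair.** There are 3 tracings at screening (criterion 16). Each Day 1 has 1 tracing if triplicates are needed only for clinically significant findings (Appendix B Table 1, footnote c), or 3 if the triplicate sentence in 6.1.2 applies throughout. With two values per tracing and n cycles:

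- lower bound: 3 × 2 + n × 1 × 2 = 6 + 2n
- upper bound: 3 × 2 + n × 3 × 2 = 6 + 6n

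The documents give no expected number of cycles, so n is an assumption.

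| Cycles assumed | Values per patient |
|---|---|
| 1 | 8 to 12 |
| 4 | 14 to 30 |
| 6 | 18 to 42 |

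For the 20 patients named in Appendix B 2.6, at 6 cycles each: 20 × 18 = 360 to 20 × 42 = 840 values.

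**2. Do 6.1.2 and Table 9 agree?**

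| QTc result | Appendix B 6.1.2 | Appendix B Table 9 | Agreement |
|---|---|---|---|
| 450-480 ms (men), 470-480 ms (women) | Stop AZD1775; may resume at reduced dose on recovery | Hold AZD1775; resume one level lower on recovery; carboplatin unchanged | Yes |
| 481-500 ms | Same rule | Hold AZD1775, cardiologist advice; no resumption rule given; carboplatin unchanged | Differs |
| 501 ms or more | Same rule | Discontinue AZD1775 and carboplatin | Contradicts |
| Shift of 60 ms or more | Same rule, with this trigger named | Discontinue AZD1775 and carboplatin | Contradicts |

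The resume sentence in 6.1.2 has no upper QTc limit, so it reaches every row. One category of four agrees, one differs and two contradict.

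**The case against.** **On the data.** Section 9.4.2.2 is a generic rule for all arms. It can be read as a method for whatever RR and QT values are reported, with the arm appendix narrowing what is captured. No text promises an Arm B QTcF table, and Section 9.5.4 leaves the safety summaries to the SAP. This softens the conflict but does not remove it: Appendix B adopts Section 9 without exception, and an analysis plan cannot create values that sites are told not to enter. If narrowing was intended, one clause should say so.

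A reader might infer that the QT signal in Arm B is lost, or that QTc monitoring is unsafe. The documents do not support that. Sites still measure QTc and act on it. An abnormal ECG can be an AE (Section 7.1), and each AE carries a verbatim term, a CTCAE grade and the action taken (Section 7.3.3), so a QT event can be told apart from other ECG findings. Scheduled ECGs are pre-dose, so the missing values are not on-drug readings taken soon after a dose. One reservation: the AE instruction in 6.1.2 itself names only unscheduled clinically significant findings.

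A reader might also take Arm C as proof that numeric values are captured elsewhere. Appendix C 7.1.3 says "The original ECG traces must be stored in the patient medical record as source data" and does not restrict eCRF entry, but it does not say that RR or QT are entered either.

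**On dosing.** The resume sentence ends with a pointer to an Appendix B table, and 7.3.3.6 points to one too, so sites are led towards Table 9. That is the best defence. It fails because neither pointer gives the table precedence over an explicit permission to resume.

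**Conclusion.** Both conflicts hold, with different weight.

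The eCRF conflict is real but confined to tabulation. As specified, no Arm B QTcF and no numeric QTcF change can come from the database. It would be too strong to say that no ECG change-from-baseline summary is possible, or that the values are irrecoverable: normal/abnormal shifts can be tabulated, and the paper tracings survive. The conclusion assumes no undescribed transfer of ECG data.

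The dosing conflict is the weightier part, because it can change what a patient receives. It is not confined to the 60 ms shift: the text and the table also contradict each other at 501 ms or more, and differ at 481-500 ms. Which action is right is a clinical decision; the finding is only that the protocol gives two.

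ORR and the rules for continuing or expanding the arm are not affected by either conflict.

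**What to change.** **ECG data.** In Appendix B 6.1.2, replace the restriction with: 'The overall evaluation, and QT and RR (or heart rate) for each tracing taken, will be recorded in the eCRF.' For patients already treated, enter the values from the retained paper tracings. The cost is two numeric fields per tracing on one eCRF page, plus entry and source verification of the values counted above; no new ECG, visit or procedure is needed. If the sponsor does not want QTcF for Arm B, the cheaper course is one clause in 9.4.2.2 exempting the arm from that derivation, at the price of reporting no QTcF values for it.

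**Dose action.** Replace the stop and resume text in 6.1.2 with a statement that QTc actions follow Appendix B Table 9, or otherwise align the two so that each QTc category has one action. All four categories need covering: aligning the 60 ms row alone would leave 481-500 ms and 501 ms or more unresolved. The same edit should say whether AZD1775 may resume after cardiologist advice at 481-500 ms, since Table 9 does not. This is a change of wording, but it needs a clinical decision from the sponsor on each row and prompt notice to sites.

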7.3.2 Dose modifications due to non-hematologic related adverse events

Dose modifications for non-hematologic toxicities should be based on toxicities occurring during the previous cycle. For toxicities that lead to a dose reduction, the dose will not be re-escalated during subsequent cycles.

Any patient who develops a Grade 3 or 4 non-hematologic toxicity that does not resolve to \leq Grade 1 within 28 days should be discontinued from the study treatment. However, if the Investigator determines that the non-hematologic toxicity was due to one study drug and not the other, treatment with the remaining study drug may continue as clinically appropriate.

Based upon the maximum non-hematologic toxicities experienced during the previous cycle, dose adjustments for subsequent cycles are to be made according to the criteria defined in [Appendix B Table 9](#) (unless specified per unique toxicities as noted below).

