7.3.3.6 QTc prolongation

The QTc interval will be measured in 12-lead ECGs at baseline and at the commencement of each treatment cycle; and an assessment made of the emergence, if any, of QTc prolongation. Serum electrolyte levels should be obtained at baseline and at commencement of each treatment cycle.

Checking and correction of abnormal electrolyte levels and renal function are advised, especially in case of diarrhoea.

The administration of AZD1775 with substances known to prolong the ECG QTc interval is not recommended.

Special note: The potential risk of concomitant use of AZD1775 with ondansetron (known to prolong the QTc interval) should be taken into account.

Dose modifications or discontinuations for patients experiencing QTc prolongations are summarized in [Appendix B Table](#) above.

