Appendix C Table 7: Management of anemia for ceralasertib plus olaparib combination

Haemoglobin	Action to be taken
Hb <10 but ≥8 g/dL (CTCAE Grade 2)	
Give appropriate supportive treatment and investigate causality.
 
Investigator judgement to continue study treatment with supportive treatment (eg transfusion) or interrupt dose for a maximum of 4 weeks.
 
If repeat Hb<10 but ≥8 g/dL, dose interrupt (for max of 4 weeks) until Hb ≥10 g/dL and upon recovery dose reduction to 250 mg BID as a first step and to 200 mg BID as a second step may be considered.

Haemoglobin	Action to be taken
Hb <8 g/dL (CTCAE Grade 3)	Give appropriate supportive treatment (eg, transfusion) and investigate causality. Interrupt study treatment for a maximum of 4 weeks until improved to Hb \geq 10 g/dL. Upon recovery dose reduce to 250 mg BID as a first step and to 200 mg BID as a second step in the case of repeat Hb decrease.

Transfusion therapy may be required to maintain Hb levels >80 g/L throughout the first three months of therapy to avoid dose reduction or interruption of olaparib. If a patient requires transfusions on a regular basis in the first 3 months, or cannot tolerate or be supported by transfusions, the dose of olaparib can be reduced.

8.4.2.2 Management of neutropenia, leukopenia and thrombocytopenia for ceralasertib plus olaparib combination

In the event of neutropenia, leukopenia or thrombocytopenia, ceralasertib and olaparib dosing should be halted until ANC and platelet count are restored to within the acceptable criteria:

- ANC 1.5×10^9 /L
- Platelets 100×10^9 /L

AEs of neutropenia and leukopenia should be managed as deemed appropriate by the Investigator with close follow up and interruption of study drug if CTC Grade 3 or worse neutropenia occurs.

Granulocyte colony-stimulating factor (G-CSF) should be used according to local prescribing guidance. Primary prophylaxis with G-CSF is not recommended, however, if a patient develops febrile neutropenia, study treatment should be stopped and appropriate management including G-CSF should be given according to local hospital guidelines. Please note that G-CSF should not be used within at least 24 hours (7 days for pegylated G-CSF) of the last dose of study treatment, unless absolutely necessary. Platelet transfusions, if indicated should be done according to local hospital guidelines. List all interventions of these types into the appropriate CRF pages.

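### The Arm B ECG section lets AZD1775 restart after a QTc shift of 60 ms or more, for which Table 9 discontinues both drugs

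*Protocol*

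**What the plan says.** **Arm B, ECG section (Appendix B 6.1.2).** The trigger sentence opens "Patients who develop a single resting value of QTc interval of >450 msec/male and >470 msec/female" and adds a shift from baseline of 60 ms or more as an alternative. Either trigger stops AZD1775. The sentence after it reads "Dosing can be resumed at a reduced dose after return of the resting QTc interval to pre-treatment status has been confirmed" and also requires any electrolyte imbalance to be corrected. It applies to both triggers alike and ends with a reference to an Appendix B table whose number is missing in the text available here.

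**Arm B, dose-modification table (Appendix B Table 9).** The row that begins "Shift from baseline of" 60 ms or more reads discontinue for carboplatin and discontinue for AZD1775. The row for 501 ms or more says the same. Holding AZD1775 and then resuming one dose level lower appears only in the row for 450-480 ms in men and 470-480 ms in women.

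**Which text governs.** Appendix B 7.3.2 says that "dose adjustments for subsequent cycles are to be made according to the criteria defined in" Table 9. Appendix B 7.3.3.6 says "Dose modifications or discontinuations for patients experiencing QTc prolongations are summarized in" the table. Master Section 4.9, which Appendix B 4.6 applies to Arm B, allows no further investigational product after an adverse event that meets a discontinuation criterion in the dose-modification guidance.

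**Arm C, blood counts (Appendix C 8.4.2.2 and Table 8).** For neutropenia, leukopenia or thrombocytopenia of any grade, the opening paragraph of 8.4.2.2 says "ceralasertib and olaparib dosing should be halted until ANC and platelet count are restored to within the acceptable criteria", namely ANC 1.5 and platelets 100 x10^9/L. The following paragraph asks only for "interruption of study drug if CTC Grade 3 or worse neutropenia occurs". Table 8 leaves Grade 1-2 to the investigator's judgement, and interrupts Grade 3-4 until recovery to Grade 1.

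**The concern.** Both Arm B texts are operative safety instructions for the same ECG finding, and they cannot both be followed. The ECG section is where an investigator looks when a tracing comes back. Someone who stops reading there gives AZD1775 again to a patient whom the protocol takes off both drugs. The situation is foreseeable: Appendix B 2.4.2 lists QT prolongation among the reported safety concerns, ECGs are required on Day 1 of every cycle, and ondansetron, which Appendix B itself notes can prolong QTc, is a named antiemetic option before each AZD1775 dose.

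Patient safety is the main stake. The second is that counts of discontinuations and dose reductions would depend on which section each site followed. The Arm C wording raises a milder form of the same problem for interruptions due to blood counts.

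**Working it through.** No sample-size or error-rate figure is involved. The check sets the rules side by side and runs single patients through them.

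**Arm B: each QTc finding under the two texts**

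| Finding | Appendix B 6.1.2, AZD1775 | Table 9, AZD1775 | Table 9, carboplatin |
|---|---|---|---|
| Above 450 ms (men) or 470 ms (women), up to 480 ms, shift under 60 ms | stop; may resume reduced | hold; resume one level lower | no change |
| 481-500 ms, shift under 60 ms | stop; may resume reduced | hold; cardiologist advice | no change |
| 501 ms or more | stop; may resume reduced | discontinue | discontinue |
| Shift of 60 ms or more | stop; may resume reduced | discontinue | discontinue |

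The texts agree fully in the first row. They contradict each other in the last two.

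**Patients who meet only the shift rule**

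- Woman, baseline 400 ms, now 462 ms: 462 - 400 = 62 ms, which is at least 60; 462 is below 470, so no absolute limit is reached. Section 6.1.2: stop, then AZD1775 at a reduced dose once QTc is back to its pre-treatment value. Table 9: both drugs discontinued.
- Man, baseline 380 ms, now 442 ms: 442 - 380 = 62 ms; 442 is below 450. The same split results.

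The 501 ms row needs no example: any such value exceeds both 450 and 470 ms, so it falls under the stop-and-resume sentence of 6.1.2 and the discontinue row of Table 9.

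**Arm C: the opening paragraph of 8.4.2.2 against Table 8**

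- Continue or halt: the upper limits come from 8.4.2.2 (ANC 1.5, platelets 100 x10^9/L) and the lower limits are the Grade 3 cuts in 8.4.2.3 (ANC below 1, platelets below 50). The conflict covers ANC 1.0 to under 1.5, or platelets 50 to under 100. A mid-cycle ANC of 1.2 halts both drugs under the opening paragraph and may continue under Table 8.
- Restart: Appendix C gives no Grade 1 cuts in numbers. Taking them from Appendix B 7.3.1 (ANC 1.5, platelets 75), the gap is 1.5 - 1.5 = 0 for ANC and 100 - 75 = 25 x10^9/L for platelets.
- Scheduled exposure: the Appendix C schedule has two mid-cycle counts, Cycle 1 Days 7 and 15; later scheduled on-treatment counts belong to Day 1 of each cycle. Unscheduled and weekly recovery counts add to this. On Day 1 there is no conflict, because Table 6 uses the same 1.5 and 100.

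**Arm B contraception.** Inclusion criterion 12 asks men for 3 months after treatment; Appendix B 4.5.1 asks for 6. The difference is 6 - 3 = 3 months.

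**The case against.** The strongest reply is that the protocol already settles the Arm B case. Section 7.3.2 puts Table 9 in charge, 7.3.3.6 sends both modifications and discontinuations for QTc to the table, and master 4.9 makes one discontinuation criterion sufficient. Section 6.1.2 sits among the assessments, is only permissive, and requires a confirmed return to pre-treatment QTc, electrolyte correction and a lower dose. Its own table reference probably points to Table 9, and the lost number may be an artefact of reading the PDF. Appendix B 2.6 plans no more than 20 eligible patients.

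Most of this stands, and it shows which text is right. It does not remove the wrong one. Section 6.1.2 states its own resumption rule for both triggers, and a pointer at the end of a sentence, numbered or not, does not withdraw what the sentence permits.

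For Arm C the reply carries more weight. Appendix C 8.4.1 assigns Table 8 to any time on treatment and Table 6 to Day 1, and the 1.5 and 100 thresholds are the Day 1 values. The opening paragraph therefore looks like a Day 1 rule without its limit, and its error is conservative, since it halts drug sooner. The platelet gap of 25 rests on a Grade 1 cut borrowed from Arm B.

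**Conclusion.** The Arm B contradiction is real and should be fixed. For a QTc shift of 60 ms or more, and for QTc of 501 ms or more, Section 6.1.2 permits a restart that Table 9 and master 4.9 rule out; Section 6.1.2 is the sentence in error. How often it would arise cannot be estimated from the document. The Arm C paragraph is a secondary, conservative inconsistency. The contraception mismatch is minor, and following the 6-month rule satisfies both texts.

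A reader might infer more than the protocol supports:

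- *That Table 9 is ambiguous when a patient meets two rows*, such as a man going from 400 to 465 ms. Under master 4.9 any one discontinuation criterion is enough, so he stops both drugs.
- *That the 481-500 ms row is defective because it gives no resumption dose.* Holding and asking a cardiologist is a workable instruction.
- *That Arm C under-reduces ceralasertib because Table 8 names only olaparib steps.* The Table 5 footnote requires both drugs to be reduced together for these toxicities, and the two tables read together give one answer.
- *That the efficacy analysis is affected.* The definition of ORR and the sample size do not depend on these rules. Tolerability enters the Review Committee's benefit-risk judgement (master 2.2.1), but the document gives no basis for sizing that effect.

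**What to change.** 1. In Appendix B 6.1.2, allow AZD1775 to resume at a reduced dose only for QTc 450-480 ms in men or 470-480 ms in women with a shift from baseline below 60 ms. State that all other cases follow Table 9, cited by number, and that any discontinuation row takes precedence.
2. In the opening paragraph of Appendix C 8.4.2.2, limit the ANC 1.5 and platelet 100 x10^9/L thresholds to Day 1 of each cycle, as 8.4.1 and Table 6 already do. Leave counts at other times to Table 8.
3. In Appendix B 4.1, change the 3 months in inclusion criterion 12 to 6 months to match 4.5.1.

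The cost is amendment text and a letter to sites. No patients are added and no analysis changes.
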